7 MANAGEMENT OF ADVERSE EXPERIENCES

Adverse Event: An adverse event is any untoward medical occurrence associated with the use of a drug in humans, whether or not considered drug related. An adverse event (also referred to as an adverse experience) can be any unfavorable and unintended sign (e.g., an abnormal laboratory finding), symptom, or disease temporally associated with the use of a drug, without any judgment about causality. An adverse event can arise from any use of the drug (e.g., off-label use, use in combination with another drug) and from any route of administration, formulation or dose, including an overdose.

Adverse Reaction: An adverse reaction means any adverse event caused by a drug. Adverse reactions are a subset of all suspected adverse reactions for which there is reason to conclude that the drug caused the event.

Suspected Adverse Reaction: Suspected adverse reaction means any adverse event for which there is a 'reasonable possibility' that the drug caused the adverse event. For the purposes of IND safety reporting, 'reasonable possibility' means there is evidence to suggest a causal relationship between the drug and the adverse event. A suspected adverse reaction implies a lesser degree of certainty about causality than adverse reaction, which means any adverse event caused by the drug. The types of evidence that would suggest a causal relationship between the drug and the adverse event include, but are not limited to:

A single occurrence of an event that is uncommon and known to be strongly associated with drug exposure (e.g., angioedema, hepatic injury, Stevens-Johnson Syndrome)

One or more occurrences of an event that is not commonly associated with drug exposure, but is otherwise uncommon in the population exposed to the drug.

An aggregate analysis of specific events observed in a clinical trial (such as known consequences of the underlying disease or condition under investigation or other events that commonly occur in the study population independent of drug therapy) that indicates those events occur more frequently in the drug treatment group than in a concurrent or historical control group.

Unexpected Adverse Event: An adverse event or suspected adverse reaction is considered 'unexpected' if it is not listed in the Investigator Brochure or is not listed at the specificity or severity that has been observed.

Serious Adverse Event: An adverse event or suspected adverse reaction is considered 'serious' if, in the view of either the Medical or Safety Monitor, it results in any of the following outcomes:

- Death
- A life-threatening adverse event
- In-patient hospitalization or prolongation of existing hospitalization
- Persistent or significant incapacity or substantial disruption of the ability to conduct normal life functions
- Congenital anomaly/birth defect

Important medical events that may not result in death, be life-threatening, or require hospitalization may be considered serious when, based upon appropriate medical judgment, they may jeopardize the subject and may require medical or surgical intervention to prevent one of the outcomes listed in this definition. Examples of such medical events include allergic bronchospasm requiring intensive treatment in an emergency room or at home, blood dyscrasias or convulsions that do not result in subject hospitalization, or the development of drug dependency or drug abuse.

Life Threatening Adverse Event: An adverse event or suspected adverse reaction is considered 'life-threatening' if, in the view of either the Investigator or Sponsor, its occurrence places the subject at immediate risk of death. It does not include an adverse event or suspected adverse reaction that, had it occurred in a more severe form, might have caused death.

Reporting a Serious Adverse Event to the Sponsor: The Investigator is required to inform the Medical Monitor by e-mail/telephone/fax within 24h of his/her becoming aware of any serious adverse event. The notification should be followed by a written report within 1 working day of such an event. The follow up observation period for the subject(s) affected will be jointly decided upon by the Investigator and the Medical Monitor. The Investigator is responsible for notification of serious adverse events to the applicable Institutional Review Board/Independent Ethics Committee (IRB/IEC). The Sponsor is responsible for all IND Safety Reporting to the US Food and Drug Administration (FDA).

Collection of Safety Information: Adverse events (AEs) and serious adverse events (SAEs) will be monitored and reported throughout the study from the time of dosing to the end of study. Each subject will be monitored for AEs throughout the study. Subjects will be asked "how are you feeling?" during each study visit and throughout the day during the residential phase of the study. AEs will be followed to resolution/stabilization, where feasible/possible, regardless of whether the subject is still participating in the study. Follow-up on AEs may include subject referrals to specialists and/or other health care providers. When applicable, the Investigator will obtain reports and/or medical records from non-study providers regarding the AE. In cases of AEs such as rashes, photographs may be taken for the purpose of documentation. Due regard for subject confidentiality will be employed.

The Investigator is not obliged to follow-up with subjects for AEs or SAEs that begin after study completion, however if an SAE is reported to the Investigator after a subject has completed the study, and it is possibly related to the study drug, then the Investigator will report it to the Sponsor.

All abnormal laboratory analytes, ECG results, vital signs and examination findings will be reviewed by the Investigator for clinical significance. If the Investigator deems a post-dose finding to be clinically significant, it will be documented as an AE. Pre-dose clinically significant findings are exclusionary. Pre-dose events will be analyzed separately from treatment emergent AEs in the final analysis.

Assessment of Adverse Events: Investigators will assess each AE based on the following definitions.

7.1 *Intensity (Severity)*

Mild: The AE is generally transient, does not interfere with usual activities, and is easily tolerated by the subject.

Moderate: The AE causes sufficient discomfort and interferes with usual activities.

Severe: The AE causes considerable interference with usual activities and may be incapacitating.

7.2 Relationship. Unrelated = None, Remote

None (unrelated, not related, no relation):

An unreasonable temporal relationship between administration of the study drug and the onset of the AE (e.g. the event occurred either before, or too long after administration of the study drug for it to be considered drug-related);

A causal relationship between the study drug and the AE is biologically implausible (e.g. death as a passenger in an automobile accident);

A clearly more likely alternative explanation for the AE is present (e.g. typical adverse reaction to a concomitant drug and/or typical disease-related event).

Remote (unlikely, doubtful, improbable):

There is little evidence to suggest there is a causal relationship and there is another reasonable explanation for the event.

7.3 Related = Possible, Probable

- Possible: There is some evidence to suggest a causal relationship (e.g. the event occurred within a reasonable time frame after administration of the study drug); however, the influence of other factors may have contributed to the event (e.g. the subject's clinical condition, other concomitant medications, or concurrent illness).
- Probable: There is evidence to suggest a causal relationship and the influence of other factors is unlikely.

Consider the following when assessing causality:

- Temporal associations between the study drug and the event
- Pre-existing risk factors or concurrent illness
- A plausible mechanism

8 CRITERIA FOR INTERVENTION DISCONTINUATION

8.1 *Intolerable Dose*

After the safety review, if the Medical Monitor, based on good clinical judgement, considers a dose level to be intolerable, then dose escalation to the next level will not proceed. Depending on the duration and potential seriousness of safety findings, the Sponsor and Investigator will determine whether the current dose level may be repeated, or if a lower dose level may be tested.

If any of the following **sentinel halting criteria** are met the rest of the cohort will not be dosed until review by the Medical and Safety Monitors, Sponsor and Investigator:

- Any subject develops a Grade 3 (severe) AE that is related to the study drug within 24 hours of dosing.
- Any subject develops an SAE related to the study drug.

The following criteria constitute specific **study halting criteria**:

- Two or more subjects experience AEs of severe intensity in the same organ class (Grade 3 according to the “Toxicity Grading Scale for Healthy Adult and Adolescent Volunteers Enrolled in Preventive Vaccine Clinical Trials,” Version September 2007) regardless of relatedness to study drug.
- One subject with a reported SAE, unless that SAE is determined to be clearly unrelated to the investigational drug product.
- Occurrence of a life-threatening allergic/hypersensitivity reaction (anaphylaxis) in any subject, manifested by bronchospasm with or without urticaria or angioedema requiring hemodynamic support with pressor medications or mechanical ventilation.
- Death of a dosed subject following dosing and prior to the subject’s last visit that was not the result of trauma or accident, regardless of relatedness to study product.
- Any other event(s) in the good clinical judgment of the responsible physician that is thought to be related to investigational product and comprises a serious risk to subject safety.

If any of the following **dose escalation halting criteria** are met escalation to the next planned dose cohort will not proceed until all available study data have been reviewed by the DSMB:

- Any subject develops an SAE related to the study drug
- Any subject experiences a Grade 3 (severe) AE related to the study drug
- 2 or more subjects in a cohort experience a Grade 2 (moderate) or greater AE that is related to the study drug and is of the same type (preferred term) and occurring in the same SOC.

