3 STUDY DESIGN

Approximately 40 healthy adult subjects, ages 18-50 years, will be dosed in 1 of 5 dosing cohorts of 8 subjects each (6 MW151, 2 matched placebo). Cohort 1 will consist of males and females; cohorts 2 – 5 will consist of females only. Each subject will receive 1 oral dose level of MW151. Five different doses of MW151 will be evaluated in 5 sequential cohorts. Dosing will start at the lowest dose, then escalate in the 2nd cohort, then escalate sequentially in the 3rd, 4th, and 5th cohorts. Plasma samples drawn at sequential time points for PK analysis; safety parameters monitored. Subjects will be followed in a dedicated inpatient unit at the clinical site, and will receive standardized meals during the Inpatient Phase.

As a safety consideration two sentinel subjects in each cohort will be administered MW151 or placebo in a 1:1 ratio.

Following review of sentinel safety and tolerability data for the first 24 hours of dosing in each cohort (including reported adverse events [AEs], physical examination findings, clinical laboratory results, vital signs, and electrocardiograms [ECGs]), the remaining 6 subjects will be randomized in a 5:1 ratio. Dosing of the remaining subjects in a cohort may proceed after review of sentinel subject safety data collected during the first 24 hours of dosing and determination that no stopping rules are met. The remaining subjects in each cohort will be dosed sequentially, not simultaneously.

After the completion of each cohort (Cohorts 1-5), the DSMB will review all available safety data before the dosing of the sentinel subjects of the next cohort. There will also be an interim PK analysis after the completion of Cohort 2.

Data from Cohorts 1-5 will be reviewed in a blinded manner, unless the findings suggest the triggering of a stopping rule, in which case the data for the subjects in question may be unblinded (e.g. if a drug related serious AE [SAE] occurs, identifying whether the subject received MW151 or placebo to determine whether the stopping rule should be triggered).

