10.2.1 Monitoring the Study Data

The conduct of the study will be monitored by the Sponsor, or designee, to ensure compliance with applicable regulatory requirements and GCP. The study monitor will maintain necessary telephone and letter contact with the Investigative site. The study monitor will verify that the study is conducted in accordance with the currently approved protocol and any amendments and will monitor subject enrolment, completeness and accuracy of subject data and reporting and recording of AEs.

The monitor will maintain current knowledge of the study through observation, review of study records and discussion of the conduct of the study with the Investigator and staff. Monitoring will be conducted according to Good Clinical Practice and applicable government regulations. The investigator agrees to allow monitors access to the clinical supplies, dispensing and storage areas, and to the clinical files of the study subjects, and, if requested, agrees to assist the monitors.

Safety monitoring will include careful assessment and appropriate reporting of adverse events. Medical monitoring will include contemporaneous assessment of serious adverse events.

The DSMB will meet after each cohort is completed or as needed, and will review subject recruitment, AE's, side effects, withdrawals, protocol violations, and inclusion/exclusion criteria. More frequent meetings will take place if necessary. Roles and responsibilities for the DSMB will be outlined in a separate DSMB charter document.

The Safety Monitor will review all adverse events, in a blinded fashion, on a periodic basis. In addition, the monitor will review all events that meet the regulatory definition of a Serious Adverse Event, upon receipt of notification via the Electronic Data Capture (EDC) system.

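### Section 8.1 triggers no automatic same-cohort hold for a single related, non-serious Grade 3 AE that starts more than 24 hours after dosing

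*Combined protocol and SAP*

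**What the plan says.** Protocol section 8.1 has three sets of halting rules, each with its own consequence.

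- **Sentinel halting criteria.** If one is met, "the rest of the cohort will not be dosed until review by the Medical and Safety Monitors, Sponsor and Investigator". There are two: "Any subject develops a Grade 3 (severe) AE that is related to the study drug within 24 hours of dosing", and "Any subject develops an SAE related to the study drug". The first carries a time limit; the second does not.
- **Study halting criteria.** The one for severe events begins "Two or more subjects experience AEs of severe intensity in the same organ class", whatever the relationship to study drug. Others cover an SAE not clearly unrelated, anaphylaxis, and a non-accidental death. The last is discretionary: "Any other event(s) in the good clinical judgment of the responsible physician that is thought to be related to investigational product", if it also amounts to a serious risk to subjects.
- **Dose escalation halting criteria.** These include "Any subject experiences a Grade 3 (severe) AE related to the study drug", with no time limit. The consequence is that the next dose cohort waits for DSMB review.

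The Synopsis, protocol section 3 and SAP 2.0 also set a gate: the other six subjects may be dosed once the sentinels' first 24 hours have been reviewed. After that, "The remaining subjects in each cohort will be dosed sequentially, not simultaneously" (section 3). No interval between subjects is given. Section 10.2.1 adds: "The DSMB will meet after each cohort is completed or as needed".

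**The concern.** This is the first trial of MW151 in humans, and subjects within a cohort are dosed one after another. Some volunteers may therefore still be undosed when an earlier subject in the same cohort has a severe event judged related to the drug. The purpose of a same-cohort hold is that such an event is reviewed before anyone else receives that dose level.

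As written, the hold depends on the hour of onset. A related Grade 3 AE at 20 hours stops further dosing in the cohort pending review. The same event at 36 hours must stop escalation to a higher dose, but need not stop dosing of the next subject at the current one. The protocol gives no reason for treating the two differently. Events after 24 hours can certainly be recorded: section 7 collects AEs from dosing to the end of the study, subjects stay in the unit until Day 3, and there is a visit on Day 7.

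**Working it through.** No power or error-rate calculation applies, and the plan gives no figure to reproduce. The check has two parts.

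**1. One test event against every rule in section 8.1.** The event: one subject, related, Grade 3, not serious, onset after 24 hours, cohort not yet fully dosed.

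| Rule | Met? | What it would hold |
|---|---|---|
| Sentinel, related Grade 3 | No: onset is after 24 hours | Rest of the same cohort |
| Sentinel, related SAE | No: not serious | Rest of the same cohort |
| Study halt, severe AEs | No: one subject, two needed in the same organ class | Whole study |
| Study halt, SAE, anaphylaxis or death | No | Whole study |
| Study halt, catch-all | Only if the physician judges it a serious risk | Whole study |
| Escalation, related Grade 3 | Yes | Next cohort only |
| Escalation, two or more related Grade 2 or worse of the same type | No: one subject | Next cohort only |
| Intolerable-dose clause | Only on the Medical Monitor's judgement | Escalation only |

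The one rule that is met without further judgement acts on the next cohort. No rule automatically holds the current one.

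This takes the 24 hours to refer to onset, which is the natural reading and matches the sentinel gate. The criterion speaks of any subject, so on its wording it continues to apply after the gate. If it were read as covering the two sentinels only, the gap would be wider: a single related, non-serious Grade 3 AE in any of the other six would then trigger no automatic same-cohort hold at any hour.

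**2. How many subjects one event could leave exposed.** Inputs are from section 3 and Table 3: after the two sentinels, six subjects per cohort, five on MW151 and one on placebo. Assume both sentinels have been dosed, and let k be the number of the six already dosed.

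- Undosed = 6 − k.
- Undosed on MW151 = 5 − k if the placebo subject is still waiting, 6 − k if that subject has been dosed.

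| k | Undosed | Of these on MW151 |
|---|---|---|
| 0 | 6 | 5 |
| 1 | 5 | 4 or 5 |
| 3 | 3 | 2 or 3 |
| 5 | 1 | 0 or 1 |
| 6 | 0 | 0 |

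The case k = 0 can arise only from a sentinel's event. If the event is in one of the six, k is at least 1. With no stated interval between subjects, the documents do not show which row would apply.

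**The case against.** The best case for the present wording is that it is a coherent choice. These are sentinel criteria, and their limit matches the 24-hour gate. Other routes to a stop exist. The catch-all halts the whole study, which is more than a cohort hold. Section 7 lets an important medical event be classed as serious on medical judgement, which engages SAE rules that have no time limit. Dosing after the gate is permitted, not required. The sponsor may stop for safety at any time (section 6.3.2), and the DSMB may meet ad hoc under a charter that is not among these documents. The proposed rule would not remove judgement either: severity and relatedness are the investigator's assessments, and section 7.3 counts a possible relationship as related.

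Much of this stands, and it limits the weight of the point. It does not close the gap. The gate decides when the six may start; the halting criterion protects whoever is still waiting afterwards. Each alternative route needs someone to decide to use it, whereas the sentinel criterion acts once the event has been graded and attributed.

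A reader might infer more than the documents support:

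- *That late severe events go unguarded.* They do not. A related SAE at any time holds the cohort, a second severe AE in the same organ class halts the study, and escalation is blocked.
- *That further subjects would receive a dose known to have caused harm.* Treatment is blinded, two of eight subjects per cohort receive placebo, and a possible relationship is enough. All that can be said is that they would be dosed at the level at which the event occurred.
- *That late events are likely.* PK sampling to 36 hours is not evidence of late toxicity. Section 2.3.1 links the QTc findings in dogs to peak concentrations, takes the testicular findings from 28-day dosing, and describes the liver enzyme and bilirubin increases as typically mild or reversible. Late events cannot be excluded without human data, but nothing here points to them.
- *That the timing of the Day 2 examinations creates the gap.* It does not, because the criterion depends on onset.

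**Conclusion.** The point holds as a narrow gap in an automatic rule. The change should be made, but the gap does not leave the trial without protection. After a single related, non-serious Grade 3 AE with onset beyond 24 hours, between zero and six subjects of that cohort (at most five on MW151) could be dosed without the section 8.1 review having to take place first.

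The conclusion rests on reading the 24 hours as time to onset, and on some of the cohort being undosed when the event appears. The reading of the text is secure. How often the situation would arise cannot be estimated, because the documents give no dosing interval and no rate of late Grade 3 AEs. A careful investigator might well pause anyway; the plan does not require it.

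**What to change.** In section 8.1, delete the last five words of the sentinel Grade 3 criterion, that is, its time limit. Any related Grade 3 AE, in any subject of the cohort and at any time, then holds all subjects of that cohort not yet dosed until the review already named there. This matches the related-SAE sentinel criterion and the Grade 3 escalation criterion. Leave the 24-hour sentinel gate in the Synopsis, section 3 and SAP 2.0 as it is; the SAP does not restate the halting criteria and needs no edit.

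The cost is one phrase in a protocol amendment, with the sponsor and IRB approval that section 6.3.2 requires, and an occasional pause in dosing within a cohort. Some pauses will follow an event in a placebo subject. Section 3 already allows the subject concerned to be unblinded when a stopping rule may have been triggered, so these can be resolved at the review.

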9 STATISTICAL CONSIDERATIONS

9.1 General Design Issues

Detailed statistical analysis plans will be created for the study and signed off in advance of database lock. One plan will be created for the analysis of PK data and a separate plan will be created for the analysis and presentation of all other study data. General statistical approaches are presented below. Baseline is defined as the last evaluation before dosing.

Safety Analysis: All subjects who receive any study treatment will be included in the safety analysis grouped by treatment received. Statistical analysis of safety data will be descriptive.

For continuous variables, summaries will include sample size, mean, standard deviation, minimum, and maximum. For categorical variables, the summaries will include frequencies and corresponding percentages. No inferential hypothesis testing will be performed on the safety variables. Repeat or unscheduled results will not be included in the summaries, but will be listed. Data from placebo subjects will be pooled for final presentations. Confidence intervals (90%, 95%) may be used in safety summaries.

Adverse Events: AEs will be coded using the Medical Dictionary for Regulatory Activities (MedDRA). AEs will be listed and summarized by treatment group and dose level. Where applicable, AEs may also be summarized by severity, seriousness, relationship to study treatment and by system organ class and preferred term. The number and percentage of subjects who experience events will be shown in the summaries. Listings for all AEs will be presented.

A treatment-emergent AE is an AE, regardless of relationship to study drug that occurs during or after the first dose of study treatment.

Laboratory Assessments: Summary statistics of observed and change from baseline data will be presented for each treatment group and dose level where applicable. Summary statistics will include number of subjects, mean, standard deviation, minimum, and maximum. Shift tables summarizing the numbers of subjects shifting from normal pre-dose values to abnormal post- dose values will also be presented where applicable. Listings for all laboratory assessments will be presented.

Vital Signs (BP, HR, Body Temperature): Summary statistics for BP and HR and change from baseline (predose) summaries will be presented for each treatment group and dose level where applicable. Summary statistics will include number of subjects, mean, standard deviation, minimum, and maximum. Listings for all vital signs will be presented.

Post-dose clinically notable vital signs will be listed and summarized by treatment and dose. Notable abnormalities are indicated in **Table 5** below:

Table 5: Criteria for Clinically Notable Vital Sign Abnormalities

Parameter	High Threshold	Low Threshold
Systolic BP (supine)	> 30 mmHg increase from baseline	> 30 mmHg decrease from baseline
Diastolic BP (supine)	> 20 mmHg increase from baseline	> 30 mmHg decrease from baseline
Heart Rate	> 120 bpm and an increase in HR of ≥ 15 bpm from baseline	< 40 bpm and a decrease in HR of ≥ 15 bpm from baseline
Body Temperature	> 39.0°C ($> 102.2^{\circ}\text{F}$)	< 35.0°C ($< 95.0^{\circ}\text{F}$)

12-Lead ECG: ECG results from the central reader will be used in the analysis. Shift tables summarizing the numbers of subjects shifting from normal pre-dose values to abnormal post-dose values will also be presented. Numeric ECG data will be summarized by treatment group and dose level and mean summary tables, including change from baseline will be presented.

The ECG results will be listed by treatment group and dose level.

Post-dose clinically notable ECGs will be listed and summarized by treatment and dose. Notable abnormalities are indicated in [Table 6](#) below:

Table 6: Criteria for Clinically Notable ECG Abnormalities

Parameter	High Threshold	Low Threshold
PR interval	PR ≥ 220 ms	PR ≤ 120 ms
QRS duration	QRS duration ≥ 120 ms and an increase of ≥ 20 ms from baseline	-
QT interval	QT interval > 500 ms	-
QTcF interval	Men: QTcF interval ≥ 450 ms and an increase of ≥ 60 ms from baseline OR QTcF interval > 500 ms Women: QTcF interval ≥ 470 ms and an increase of ≥ 60 ms from baseline OR QTcF interval > 500 ms	-

Pharmacokinetic Analysis: The plasma concentrations of MW151 will be determined, and used to estimate appropriate PK parameters including C_{max} , T_{max} , AUC, $T_{1/2}$ and K_{el} by non- compartmental analysis. The PK analysis population will include all subjects who received the active study drug and who have sufficient MW151 plasma concentrations to calculate at least 1 PK parameter.

PK parameters will be listed for each individual subject and summarized for each dose level; the summary will consist of number of subjects, arithmetic mean, standard deviation, and geometric mean, coefficient of variation, minimum, median, and maximum. Profiles for each subject will be presented graphically. Additionally, a mean profile will be presented by treatment group and dose level.

The PK analysis will be conducted at a facility selected by the Sponsor. PK data will be provided to the Sponsor for inclusion into the final clinical study report.

